**Assessing the Utility of MMPI-2-RF-EX in Detecting Simulated Underreporting of
Current Suicide Risk in Military Veterans**

NCT: 2020B0414

Study Protocol and Statistical Analysis Plan

Approved 2/25/2021

Assessing the Utility of MMPI-2-RF-EX in Detecting Simulated Underreporting of Current Suicide Risk in Military Veterans

1. Objectives

The aims of the current project are: 1) to examine the incremental predictive utility of the MMPI-2-RF-EX validity scales (L and K) in detecting simulated underreporting of suicide risk on the SUI scale and extratest measures of suicide risk (Suicide Cognitions Sale, Beck Scale for Suicide Ideation – Current) and 2) compare the use and preliminary effectiveness of a self-administered version of the Crisis Response Plan (CRP) in decreasing suicidal/death ideation and distress and increasing positive affect when compared to a clinician-administered version of the protocol in a sample of 150 military Veterans experiencing current death or suicidal ideation. Hypotheses include: **(H1)** Veterans following instructions to underreport suicide risk (Simulated Underreporting) would endorse significantly higher MMPI-2-RF-EX L and K scale scores than those administered the MMPI-2-RF-EX and extra test measures under standard conditions (Standard Instructions); **(H2)** Veterans randomized to the Simulated Underreporting group will produce significantly lower scores on MMPI-2-RF-EX (SUI) and extra test self-report measures of suicide risk (Suicide Cognitions Scale, Beck Scale for Suicide Ideation – Current) than the Standard Instructions group; **(H3)** lastly, L and K would contribute incremental predictive validity over one another in differentiating between veterans in the Standard Instructions and Simulated Underreporting group. Exploratory analyses will be conducted to examine whether those randomized to Simulated Underreporting endorse lower mean scores on extratest measures that do not assess suicide risk.

2. Background and Rationale

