Online recruitment methods for the study are include web-based survey and research recruitment systems (e.g., SurveyMonkey), listservs and forums, and social media sites (e.g., Facebook, Twitter, Reddit). Additionally, we are requesting use of ResearchMatch (RM), which is an NIH sponsored national registry for research volunteers. ResearchMatch (RM) and OSU have had a fully executed agreement since August 2009. The IRB of record for ResearchMatch is Vanderbilt University. The Principal Investigator will be authorized to recruit study participants.

We will enroll any prospective Veteran meeting inclusion criteria (18 years of age or older, US military veteran, death or suicidal ideation/suicide attempt within the past month) in the proposed study. Exclusion criteria include: non-Veteran status, acute intoxication or active psychosis precluding

provision of informed consent, an inability to communicate and comprehend English, residence outside the United States, and lack of past-month death/suicide ideation or attempt. Participants recruited through web-based survey and research and recruitment systems will provide consent for study personnel to initiate contact through email or phone call, while those recruited through other online methods (e.g., listservs, forums) will be provided contact information for study personnel in order to inquire about the study or schedule participation.

3.3 Measurement/Instrumentation. The following self-report measures will be administered through Qualtrics online survey software during baseline procedures as part of the proposed research:

MMPI-2-RF-EX. The MMPI-2-RF-EX The MMPI-2-RF-EX was developed for research purposes in order to develop the MMPI-3 (Ben-Porath & Tellegen, 2020), which is comprised of a subset of MMPI-2-RF-EX items. While completing the MMPI-2-RF-EX, all participants will be monitored remotely by study personnel using a web camera and OSU CarmenZoom to ensure test integrity, as required by the study funding agency. While completing the MMPI-2-RF-EX, participants will simultaneously select the MMPI-2-RF-EX item numbers corresponding to those they believe are assessing current suicide risk through a separate internet browser or tab opened to a link in Qualtrics provided by study personnel.

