Suicide Cognitions Scale (SCS; Bryan et al. 2014). The SCS is an 18-item survey measuring suicide-related thoughts and beliefs, unclouding hopelessness, perceived burdensomeness, entrapment, and unbearability. Respondents rate their agreement with each statement on a 5-point Likert scale. Item responses are summed, with higher scores indicating more severe suicide risk.

Beck Scale for Suicide Ideation-Current (BSS; Beck & Steer, 1991). The BSS is a 21-item measure of past-week suicide ideation and desire for death. Responses to items are scored on a 3-point Likert scale (range of 0- 2), with higher scores indicating greater suicide risk.

Short Grit Scale (Duckworth & Quinn, 2009). The Short Grit Scale is being administered to examine whether those randomized to the Simulated Underreporting condition endorse lower mean scores when compared to those randomized to the Standard Instructions condition (e.g., whether simulated underreporting of suicide risk extends to extratest measures that do not explicitly measure suicide risk).

PTSD Checklist for DSM-5 (PCL-5; Weathers et al., 2013). The PCL-5 is a self-report measure assessing the severity of 20 PTSD symptoms. Respondents rate the severity of each symptom during the past week on a 5-point Likert Scale ranging from 0 (*Not at all*) to 4 (*Extremely*). Similar to the Short Grit Scale, the PCL-5 is being administered to examine whether Veterans in the Simulated Underreporting groups endorse lower mean scores than those in randomized to the Standard instructions group.

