3.4. Informed Consent and Confirmation of Eligibility

Informed consent will be obtained through Qualtrics survey software from each participant prior to initiation of study tasks. Study personnel will obtain informed consent from participants and answer questions about the study or informed consent process prior to beginning study activities. Following informed consent, participants will complete a demographics questionnaire through Qualtrics that also includes items assessing history of suicide attempts from the Self-Injurious Thoughts and behaviors Interview (Nock, Holmberg, Photos, & Michel, 2007) for study eligibility determination and randomization purposes as well as the Suicide Visual Analog Scale (Bryan, 2019). Regardless of eligibility, all participants will be provided with contact information for crisis resources including the National Suicide Prevention Lifeline and Veterans Crisis Line.

3.5. Randomization to Study Conditions.

REDCap, a secure online survey and data management system maintained by The Ohio State University, will be utilized to randomize participants to study conditions immediately after obtaining demographic information (man, woman, other) and information about suicide attempt history (no suicide attempts, one suicide attempt, more than one suicide attempt) obtained from the SITBI). Participants will be randomized using stratified blocks of 6 or 8 participants, per recommendations by Krenan et al. (1999). After randomization, each participant will complete the remainder of the research study, but will be presented with one of the following pages containing instructions for completing the MMPI-2-RF-EX.

MMPI Condition 1 (Standard Instructions): “We want you to imagine that you are undergoing psychological testing as part of standard intake procedures for receiving services in a mental health clinic, which involves completing some questionnaires and a personality test before the first session. Please answer the questionnaires as honestly as you can, as your mental health care provider will use the results of your testing to develop your treatment plan. Please note, the questionnaire has some “lie” scales built into it that detect false responding. Additionally, as part of the intake process, you agreed to identify questions that you think are assessing your current risk of suicide. You will open the link to this portion of the study that was sent to you by study personnel to complete this.”

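### Past-month entry does not match the past-week BSS or the stated aim of current risk, so the BSS part of H2 is diluted by an unmeasured amount

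*Combined protocol and SAP*

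**What the plan says.** Section 3.2 sets the entry rule as "death or suicidal ideation/suicide attempt within the past month". The only matching exclusion is "lack of past-month death/suicide ideation or attempt". No past-week or present-day criterion appears.

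Section 1 describes the aims "in a sample of 150 military Veterans experiencing current death or suicidal ideation", and the title also refers to current risk. H2 predicts that simulators will produce "significantly lower scores on MMPI-2-RF-EX (SUI) and extra test self-report measures of suicide risk (Suicide Cognitions Scale, Beck Scale for Suicide Ideation – Current").

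Section 3.3 gives a recall window for only one of these three outcomes: "The BSS is a 21-item measure of past-week suicide ideation and desire for death". Its items are scored from 0 to 2. For the SCS it says "The SCS is an 18-item survey measuring suicide-related thoughts and beliefs" and states no window. None is stated for SUI.

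Section 3.4 collects attempt history before randomisation, "as well as the Suicide Visual Analog Scale", whose time frame is not given. Sections 3.1 and 3.5 stratify on gender and lifetime attempt history. Section 3.8.1 tests H2 with a one-way MANOVA between arms and names no ideation covariate or subgroup.

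**The concern.** A Veteran whose ideation ended between 8 and 30 days ago is eligible, yet lies outside the BSS window. The Standard arm is told to answer honestly, so such a person should score at or near zero on the BSS, provided there was also no desire for death in the past week. A simulator in the same position cannot go lower. The scenario in section 3.5 does not change this, because it asks simulators to hide suicidal thoughts, which also leads to a score near zero.

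These participants sit in both arms and contribute almost no BSS difference. The observed contrast therefore understates how far concealment lowers the BSS in people who have something to conceal. A small or null result could mean weak concealment or little to conceal. The planned analysis does not separate the two.

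**Working it through.** **1. The plan's own power figure.** Section 3.2 states .98–.99 (labelled beta) for medium effects in the regression analyses at N = 150. With assumed f² = 0.15 and alpha 0.05, noncentrality f² × N = 0.15 × 150 = 22.5, the noncentral F gives 0.992 with two predictors and 0.985 with three. The figure reproduces. It covers the regressions only; no power is stated for the H2 mean comparison.

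**2. Inputs for the BSS comparison.**
- From section 3.2: 75 per arm, and an allowance of roughly 15% for invalid responding, which leaves about 64 per arm (75 × 0.85 = 63.75).
- Assumed: two-sided alpha 0.05; d = 0.5 among participants with past-week ideation or desire for death; zero effect in the remaining share q; common SD. Neither d nor q is in the documents.

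**3. Simple dilution.** Overall effect = (1 − q) × d. Power is from the noncentral t with noncentrality d × √(n/2). The restricted comparison keeps d = 0.5 with n = 75 × (1 − q).

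| q | Diluted d | Power, 75 per arm | Power, 64 per arm | Restricted n per arm (from 75) | Restricted power |
|---|---|---|---|---|---|
| 0 | 0.50 | 0.86 | 0.80 | 75 | 0.86 |
| 10% | 0.45 | 0.78 | 0.71 | about 68 | 0.82 |
| 25% | 0.375 | 0.63 | 0.56 | about 56 | 0.75 |
| 40% | 0.30 | 0.45 | 0.39 | 45 | 0.65 |

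**4. Allowing for the floor's effect on the variance.** Put the share q at exactly zero in both arms. Let Standard-arm ideators have a mean of m SDs and simulating ideators m − 0.5. The arm variances, in ideator SD² units, are (1 − q) + q(1 − q)m² and the same with m − 0.5 in place of m. The standardised effect is (1 − q) × 0.5 divided by the square root of their average. For m from 1 to 2, power at 75 per arm is:
- q = 10%: 0.80 to 0.71
- q = 25%: 0.69 to 0.51
- q = 40%: 0.56 to 0.35

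The restricted comparison (0.82, 0.75, 0.65) remains better in each case, though at q = 10% and m = 1 the gain is only about 0.02.

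**5. If the effect is large.** With d = 0.8 among past-week ideators and q = 30%, the simple diluted effect is 0.56 and power at 75 per arm is still 0.93.

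**The case against.** The strongest reply has five parts.

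- **Only one of three H2 outcomes is affected.** A reader might infer that H2 as a whole is diluted because these participants have nothing to underreport. The documents do not support that. No past-week window is given for SUI or the SCS, and the SCS covers beliefs such as hopelessness and burdensomeness that someone with ideation three weeks ago may still hold and hide. This objection stands, and the point is limited to the BSS.
- **The floor is not automatic.** The BSS also counts desire for death, so absence of suicidal ideation alone does not put a participant near zero. This stands; only those with neither in the past week are meant.
- **Existing data help.** The Posttest Inquiry asks whether participants tried to look not suicidal, and the honest Standard arm would show roughly what share sits at the BSS floor. Randomisation makes that share comparable across arms. This stands in part: it would gauge the dilution after the fact. It cannot identify which simulators had past-week ideation, because their BSS answers are distorted by design. A direct restricted comparison therefore needs a pre-randomisation variable.
- **The comparison is valid as it is.** A reader might also infer bias between arms. There is none: randomisation protects the contrast, which estimates the effect of the instructions in the population enrolled. A month is also a defensible reading of current, and section 2.3 speaks more loosely of current distress or suicidal ideation. This stands.
- **Restriction can cost power.** If SUI and SCS respond across the whole sample, restricting them discards information. At d = 0.5, going from 75 to 45 per arm takes power from 0.86 to 0.65. This stands, and it is why the restricted analysis should be confined to the BSS.

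**Conclusion.** The concern holds for the BSS. The entry window (past month), the stated population (current ideation) and the BSS window (past week) do not match, and neither the stratification nor the analysis addresses it. The consequence is a smaller BSS effect estimate, lower power for that outcome, and a small or null BSS difference that is hard to interpret.

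The size is conditional. The drop from 0.86 to between 0.78 and 0.45 rests on assumed d = 0.5, two-sided alpha 0.05, 75 per arm, and q between 10% and 40%. The loss is small if q is about 10% or if the true effect is large. The documents do not show an underpowered H2 overall, and the mismatch does not bear on the power stated for the regressions. It warrants a cheap improvement, not a redesign.

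**What to change.** 1. Add one yes/no item on past-week death or suicidal ideation to the pre-randomisation survey in section 3.4. Eligibility can stay as written.
2. In section 3.8.1, pre-specify a BSS comparison between arms among participants answering yes, reported beside the full-sample result. Because the item precedes randomisation, restricting on it keeps the randomised comparison.
3. Keep the full-sample comparison as the main one for H2, including SUI and SCS. Label the restricted BSS result as supportive, so that it adds no confirmatory test.
4. If no item can be added, use the pre-randomisation Suicide Visual Analog Scale score as a baseline covariate in the H2 comparison, and note that its time frame is not stated. This keeps every participant and may recover precision, but the estimate remains an average over people with and without past-week ideation.

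The cost is one survey item, a few lines of analysis plan, and fewer participants in the restricted comparison (about 68, 56 or 45 per arm at q = 10%, 25% or 40%, before invalid-response exclusions). The item also reveals q, which the plan as written does not measure before randomisation.

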2.1.2 The MMPI in detecting underreporting and its extension to extratest measures

A growing body of evidence indicates that underreporting on the MMPI instruments generalizes to conjointly administered self-report measures. Forbey and Lee (2011) observed that individuals who produced significantly elevated MMPI-2 K and L scale scores endorsed significantly lower mean scores on several conjointly administered self-report measures assessing various symptoms of psychopathology with roughly medium to large sized effects. Additionally, Forbey and colleagues (2013) observed that scores on internalizing self-report measures, namely the Beck Depression Inventory (Beck, Ward, Mendelson, Mock, & Erbaugh, 1961), were also significantly lower for the content-based underreporting group with medium to large effects. Indeed, individuals indicated as underreporting on the MMPI-2 and MMPI-2-RF respond in a similar manner to extratest measures of psychopathology in university, VA psychiatric inpatient, and correctional settings (Forbey & Lee, 2011; Forbey et al., 2013).

Underreporting may result in false negative findings, particularly in high-stakes assessments (Crighton, Marek, Dragon, & Ben-Porath, 2017). However, limited quantitative research has focused on identifying underreporting in suicide risk assessment, a limitation noted in the current research base (Burchett and Ben-Porath, 2019). Indeed, preliminary evidence indicates that underreporting on the MMPI-2 may have implications for suicide risk assessment. During clinic intake procedures, individuals who denied current suicide ideation/behavior on both a clinician-administered phone interview and the MMPI-2 produced higher K, S, and ODep scores than those who responded affirmatively to only MMPI-2 questions or both the interview and MMPI-2 items (Glassmire, Stolberg, Greene, & Bongar, 2001). However, no research has extended this research to Veterans outside of the VA setting or examined whether the MMPI-2-RF-EX possesses similar clinical utility of previous iterations of the MMPI to accurately identify Veterans who underreport current suicide risk.

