MMPI-based research involving simulation designs have indicated the need for including indicators of underreporting when administering extratest self-report measures. Such research designs allow examination of the construct validity of the MMPI across response-style groups while maintaining experimental control over study conditions (Burchett & Ben-Porath, 2019; Dhillon, Bagby, Kushner, & Burchett, 2016). Sellbom and Bagby (2008) examined the impact of simulated underreporting on MMPI-2-RF substantive scales in undergraduate students and individuals with schizophrenia and observed that K-r and L-r added incrementally to each other in predicting underreporting in both groups, with greater effects in those diagnosed with schizophrenia. These findings were replicated in undergraduate students (Creighton et al., 2017). Other research utilizing simulation designs have noted differences in extratest measures of trait negative affectivity (Dhillon, Bagby, Kushner, & Burchett, 2016). Despite the need for research assessing whether underreporting negatively impacts the sensitivity of suicide risk assessment through simulation research designs (Burchett & Ben-Porath, 2019; Rogers, 2018), such research has not been conducted. **This research is particularly timely for populations at heightened risk of suicide - including Veterans. The proposed study addresses this absence in the research base by employing a simulation design centered on explicit underreporting of suicide risk to identify how Veterans respond to SUI and other MMPI-2-RF-EX scales when intending to conceal suicidal ideation or intent.**

Additionally, this study design affords the additional advantage of comparing SUI scores and scores of extratest measures of suicide risk between those attempting to underreport suicide risk and those testing under standard instructions.

2.3 Anticipated Results and Potential Pitfalls It is anticipated that this research will advance the detection and treatment of suicide risk among military veterans who seek clinical services outside the Veterans Affairs setting. More specifically, based on the aforementioned findings regarding the MMPI, we anticipate that the MMPI-2-RF-EX will demonstrate clinical utility in detecting simulated underreporting of suicide risk among individuals with current distress or suicidal ideation.

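### Does the missing scoring direction for the Short Grit Scale put the wrong sign on the exploratory comparison?

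*Combined protocol and SAP*

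**What the plan says.** Section 3.3 gives the purpose of the Short Grit Scale and little else: "The Short Grit Scale is being administered to examine whether those randomized to the Simulated Underreporting condition endorse lower mean scores". It explains this as a check on "whether simulated underreporting of suicide risk extends to extratest measures that do not explicitly measure suicide risk". The PCL-5 entry applies the same direction: "Similar to the Short Grit Scale, the PCL-5 is being administered to examine whether Veterans in the Simulated Underreporting groups endorse lower mean scores". Section 1 puts the question under exploratory analyses, asking whether simulators "endorse lower mean scores on extratest measures that do not assess suicide risk", and names no measure.

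The other extratest scales in Section 3.3 can be read without outside help. The SCS is described "with higher scores indicating more severe suicide risk" and the BSS "with higher scores indicating greater suicide risk". The PCL-5 items run from 0 to 4 in severity. Section 3.8.1 lists the Short Grit Scale beside the PCL-5 under a psychopathology label and enters both, with L, K, SUI, BSS and SCS, in a one-way MANOVA comparing the two arms. Apart from Sections 3.3 and 3.8.1, the scale appears only in the bibliography.

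**The concern.** A lower score signals underreporting only where a high score means something worse. For the SCS, BSS and PCL-5 the plan shows that this is so. For the Short Grit Scale it does not, and the name suggests a strength, not a symptom. If higher means more grit, a person presenting favourably would score higher, and the direction written in Sections 1 and 3.3 would be backwards for this scale.

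The cited background does not fill the gap. Section 2.1.2 reports that people with elevated K and L "endorsed significantly lower mean scores on several conjointly administered self-report measures assessing various symptoms of psychopathology", and adds: "Other research utilizing simulation designs have noted differences in extratest measures of trait negative affectivity". The first concerns symptoms, the second a negative trait.

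At stake is the reading of one of only two named measures that address whether underreporting spreads beyond suicide risk. A real spread could be taken for its absence or its opposite.

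**Working it through.** **The plan's own figure.** The only design figure is the power of .98 to .99 in Section 3.2 (printed as beta) for medium effects in the regression analyses. Taking f² = 0.15 and two-sided alpha 0.05 (both assumed, as neither is stated), the noncentrality is 0.15 × 150 = 22.5. The power is then .997 with one predictor, .992 with two and .985 with three. This is close to the stated range. Those regressions use K and L only (Section 3.8.1), so Grit scoring cannot affect them.

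**Does the direction affect the planned test?** There are seven outcomes (L, K, SUI, BSS, SCS, PCL-5, Grit), two groups and N = 150.

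- Wilks' lambda is Λ = |E| / |E + H|, where E and H are the within-group and between-group sums-of-squares matrices.
- Reverse-scoring replaces a score x by c − x. The constant c drops out of the deviations. The sign change replaces E by DED and H by DHD, where D is diagonal with one entry of −1 and the rest 1.
- Since |D|² = 1, |DED| = |E| and |D(E + H)D| = |E + H|. Λ is unchanged.
- Numerical check on simulated data, 75 per arm: Λ = 0.7647 with either sign. The degrees of freedom are 7 and 150 − 7 − 1 = 142. F = (1 − 0.7647)/0.7647 × 142/7 = 6.241 both times.

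A two-sided univariate follow-up on Grit behaves likewise: the mean difference changes sign and its size and p-value do not.

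**Where could direction matter?** Only in a one-sided follow-up, which the plan does not specify. With an assumed d = 0.5, 75 per arm and one-sided alpha 0.05, the noncentrality is 0.5 × √(75/2) = 3.06. Power is .92 in the right direction and below .001 in the wrong one. This would be a serious loss, but in a test nobody has proposed.

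**Can the size of a sign error be estimated?** Suppose a true favourable shift of d, with z = d√(n/2) and n = 75.

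| d (assumed) | z | P(simulator mean lower) if higher = more grit | if higher = worse |
|---|---|---|---|
| 0.2 | 1.225 | 0.110 | 0.890 |
| 0.5 | 3.062 | 0.001 | 0.999 |

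The last two columns sum to 1 in each row. They repeat the two scoring assumptions and give no evidence on which is true.

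**What do the documents say about the two assumptions behind a reversal?**

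1. *Higher means more grit.* No section says so. The only description, in Section 3.8.1, classes the scale with psychopathology; on that reading a lower score is the coherent sign. The label is a hint and not a scoring rule.
2. *Simulators present favourably in general.* The Section 3.5 instructions ask them to conceal suicidal thoughts and intent while evading the lie scales. Section 3.6 pays a further $20 to compliant simulators who avoid clinically significant K or L elevations. Both give simulators a reason not to look good across the board, so the direction of any Grit shift is itself open.

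**The case for a change.** The best argument for a change is that the gap is real and cheap to close. Short Grit is the only one of the four extratest scales whose direction cannot be read from the plan, yet a direction is attached to it. The exploratory question in Section 1 is itself directional, so a non-directional MANOVA does not fully answer the point: someone must still decide whether an observed difference counts as underreporting spreading. On either scoring a sentence is missing, and if higher does mean more grit, the psychopathology label in Section 3.8.1 is also loose.

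The omission therefore stands, and so does the possibility that the wording was carried over from symptom scales. The claim that the sign is wrong does not, because it needs a scoring rule that the documents do not contain. Nor does the plan predict a lower Grit mean in the way that H1 and H2 make predictions; it asks whether one occurs. The decision about meaning can be made when the scale is scored. The instrument's source is cited in Section 3.3, and no mean can be computed without a scoring rule.

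**Conclusion.** No change to the plan is needed. This is a missing descriptive detail that analysts will fill sensibly. It touches one of seven MANOVA outcomes and one of two named exploratory measures. No test statistic, power figure or conclusion on H1 to H3 depends on it, and the size of the Grit difference is the same whichever way the scale runs.

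The conclusion rests on two conditions: that Grit follow-up comparisons are two-sided, since the plan specifies no one-sided test, and that the analysts score the instrument from its cited source. Whether a lower mean is the right sign cannot be decided from these documents. Stating the meaning of a high Grit score when results are reported would be good practice, but it would not alter the design or the analysis.
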